### Primary Efficacy Endpoints:

#### Distance Monocular LogMAR Visual Acuity (VA)

Distance monocular logMAR VA will be assessed for each subject eye at the two-week follow-up evaluation using ETDRS charts at 4 meters under high luminance high contrast (HLHC) condition.

#### CLUE Overall Quality of Vision

Subjective overall quality of vision will be assessed using Contact Lens User Experience (CLUE) questionnaire. CLUE is a validated patient-reported outcomes questionnaire to assess patient-experience attributes of soft, disposable contact lenses (comfort, vision, handling, and packaging) in a contact-lens wearing population in the US, ages 18-65. Derived CLUE scores using Item Response Theory (IRT) follow a normal distribution with a population average score of 60 (SD 20), where higher scores indicate a more favorable/positive response. A 5-point increase in an average CLUE score translates into 10% shift in the distribution of scores for population of soft disposable contact lens wearers.

**Secondary Endpoint(s):** The following endpoints are defined in [REDACTED]

### Secondary Efficacy Endpoints:

#### CLUE Overall Handling

Overall handling will be assessed using Contact Lens User Experience (CLUE) questionnaire.

# Clinical Study Protocol

## Johnson & Johnson Vision Care, Inc.

### CLUE Overall Comfort

Overall comfort will be assessed using Contact Lens User Experience (CLUE) questionnaire.

### Situational Visual Performance – Indoors

Situation visual performance – indoors will be assessed using the individual item “Clarity of vision indoors in bright light” ( [REDACTED] ). This item uses a 5-point Likert response scale, 1: Excellent, 2: Very Good, 3: Good, 4: Fair and 5: Poor.

### Situational Visual Performance – Digital Devices

Situation visual performance – digital devices will be assessed using the individual item “Overall preference while using computer screens & digital devices” ( [REDACTED] ). The response set for this preference item include: Strongly prefer my habitual lenses, Slightly prefer my habitual lenses, No preference, Slightly prefer the study lenses, and Strongly prefer the study lenses.

### **2.3. Hypotheses**

All the following primary hypotheses must be met for the objectives of this study to be satisfied:

#### Primary Hypotheses

##### Safety

1. The JJVCI investigational contact lens is non-inferior to the control lens with respect to the proportion of eyes with clinically significant slit lamp findings across all study visits. A non-inferiority margin of 5% will be used.
2. The JJVCI investigational contact lens is non-inferior to the control lens with respect to the proportion of eyes with unacceptable lens fitting at dispensing and follow up visit. A non-inferiority margin of 10% will be used.

##### Efficacy

1. The JJVCI investigational contact lens is non-inferior to the control lens with respect to monocular high luminance, high contrast distance visual acuity at the follow-up visit. A non-inferiority margin of 0.05 logMAR will be used.
2. The JJVCI investigational contact lens is non-inferior to the control lens with respect to overall CLUE vision score at the follow up visit. A non-inferiority margin of -5 points on the CLUE scale will be used.

# **Clinical Study Protocol**

## **Johnson & Johnson Vision Care, Inc.**

### Secondary Hypotheses

#### Efficacy

1. The JJVCI investigational contact lens is non-inferior to the control lens with respect to overall CLUE handling score at the follow-up visit. A non-inferiority margin of -5 points on the CLUE scale will be used.
2. The JJVCI investigational contact lens is non-inferior to the control lens with respect to overall CLUE comfort score at the follow-up visit. A non-inferiority margin of -5 points on the CLUE scale will be used.
3. The JJVCI Investigational contact lens will be non-inferior to the Control lens with respect to the proportion of subjects with Excellent responses to the statement “Clarity of Vision indoors in bright light (████████)” at the follow-up visit. A non-inferiority margin of 0.67 for odds ratio will be used.
4. The JJVCI Investigational contact lens will be superior to the Control habitual lens with respect to overall preference while using computer screens & digital devices at the follow up visit.

### **3. TARGETED STUDY POPULATION**

#### **3.1. General Characteristics**

Approximately 160 subjects will be targeted to the Test Group and approximately 160 will be targeted to the Control Group. Within each lens group, the intent is to complete 143 (286 total subjects). Enrolled subjects will be habitual wearers of silicone hydrogel spherical contact lenses. All subjects will be the age of  $\geq 18$  and  $< 40$ . Subjects will wear the study contact lenses approximately two weeks each on a daily wear (DW) daily disposable (DD) basis for a total study duration of approximately 14 days (2 weeks) per subject.

#### **3.2. Inclusion Criteria**

Potential subjects must satisfy all of the following criteria to be enrolled in the study:

##### Inclusion Criteria after Screening

The subject must:

1. Read, understand, and sign the STATEMENT OF INFORMED CONSENT and receive a fully executed copy of the form.
2. Appear able and willing to adhere to the instructions set forth in this clinical protocol.
3. Be between 18 and 39 (inclusive) years of age at the time of screening.
4. By self-report, habitually wear spherical silicone hydrogel soft contact lenses in both eyes in a daily reusable or daily disposable wear modality (i.e. not extended wear modality). Habitual wear is defined as a minimum of 6 hours of wear per day, for a minimum of 5 days per week during the past 30 days.
5. Have a habitual contact lens prescription that is current within the prior 6 months, and they must have worn that prescription for at least 2 weeks prior to entering the study.

# **Clinical Study Protocol**

## **Johnson & Johnson Vision Care, Inc.**

### Inclusion Criteria following Baseline Evaluation

6. The subject's vertex corrected spherical equivalent distance refraction must be in the range of -1.00 through -6.00 D in both eyes.
7. The subject's refractive cylinder must be 1.00 D or less.
8. The subject must have best corrected visual acuity of 20/25 or better in each eye.

### **3.3. Exclusion Criteria**

Potential subjects who meet any of the following criteria will be excluded from participating in the study:

#### Exclusion Criteria after Screening:

The subject must not:

1. Be currently pregnant or lactating.
2. Have any ocular or systemic allergies or diseases that may interfere with contact lens wear.
3. Have any autoimmune disease or use of medication, which may interfere with contact lens wear. Habitual medications used by successful soft contact lens wearers are considered acceptable.
4. Have any previous, or planned, ocular or interocular surgery (e.g., radial keratotomy, PRK, LASIK, etc.).
5. Be currently wearing lenses in a monovision, multi-focal, toric, or extended wear modality.
6. Have participated in a contact lens or lens care product clinical trial within 14 days prior to study enrollment
7. Be an employee (e.g., Investigator, Coordinator, Technician) or immediate family member of an employee (including partner, child, parent, grandparent, grandchild or sibling of the employee or their spouse) of the clinical site.
8. Have a history of binocular vision abnormality or strabismus.
9. Have any infectious disease (e.g., hepatitis, tuberculosis) or contagious immunosuppressive diseases (e.g., HIV) by self-report.

#### Exclusion Criteria at Baseline Evaluation

The subject must not:

10. Have any Grade 3 or greater slit lamp findings (e.g., edema, corneal neovascularization, corneal staining, tarsal abnormalities, conjunctival injection) on the FDA classification scale, any previous history or signs of a contact lens-related corneal inflammatory event (e.g., past peripheral ulcer or round peripheral scar), or any other ocular abnormality that may contraindicate contact lens wear.
11. Have any ocular infection.
12. Have any corneal distortion resulting from previous hard or rigid gas permeable contact lens wear.

# **Clinical Study Protocol**

## **Johnson & Johnson Vision Care, Inc.**

13. Have entropion, ectropion, extrusions, chalazia, recurrent styes, glaucoma, history of recurrent corneal erosions, or aphakia.

### **3.4. Enrollment Strategy**

Study subjects will be recruited from the Institution/clinical site's subject database and/or utilizing Independent Ethics Committee (IEC) or Institutional Review Board (IRB) approved materials.

The overall goal is to enroll approximately 320 eligible subjects and complete 286 that are evenly distributed between the Test Group and the Control Group (Table 1).

Table 1: Enrollment Strategy Overall

Overall Enrollment	Strata	Test Group	Control Group	Total
Randomized	Overall	143-160	143-160	286-320
	Habitual Daily Disposable	~112	~112	~224
	Habitual Daily Wear Reusable	~48	~48	~96
Completed	Overall	143	143	286
	Habitual Daily Disposable	~100	~100	~200
	Habitual Daily Wear Reusable	~43	~43	~86

Approximately 16 sites are expected to enroll approximately 20 subjects each with approximately 10 subject wearing the Test lens and approximately 10 wearing the Control lens during the study. Habitual wearers of daily disposable lenses will be preferentially targeted in a 7:3 ratio over habitual wearers of daily wear reusable lenses in each lens group within each site (i.e., 7 habitual wearers of daily disposable lenses versus 3 habitual wearers of daily wear reusable lenses).

## **4. STUDY DESIGN AND RATIONALE**

### **4.1. Description of Study Design**

This study is a controlled, randomized, subject-masked, 2-arm parallel, 2-week dispensing, bilateral evaluation where the study lenses are worn for a minimum of 5 days per week and 6 hours per day. At study closure, participants will have no further access to the Test lenses.

The study begins with an initial visit (Visit 1). If a subject is found to meet all eligibility criteria, then they will be randomized and fit with either the Test or Control lenses in both eyes; otherwise, a subject will be deemed ineligible for this study. If the subject is dispensed study

# **Clinical Study Protocol**

## **Johnson & Johnson Vision Care, Inc.**

lenses at the initial visit, a follow-up visit will be conducted. The follow-up visit will occur approximately 2 weeks after the initial visit. Unscheduled visits may occur during the study.

### **4.2. Study Design Rationale**

The purpose of this study is to evaluate the performance of a new UV/HEV-filter in a 2-arm parallel design. In this parallel design, subjects are randomized to one of the two study arms and after randomization each participant will stay in their assigned treatment arm for the duration of the study. Randomization eliminates the selection bias and balances both the known and unknown confounding factors that may affect the study outcomes.

### **4.3. Enrollment Target and Study Duration**

This study will have an enrollment target of 320 subjects, with a target of at least 286 to complete. The study will be conducted at up to 16 clinical sites, where the enrollment target for each site will be approximately 20 subjects. A subject will be considered enrolled upon signing of the informed consent form.

There will be 2 visits in total per subject; total study duration including the enrollment period is expected to be approximately 6 weeks. Subjects who are discontinued prior to the final evaluation may be replaced at the discretion of the study sponsor. The investigation will end at the time that the study data is hard locked.

Table 2: Duration of Study Visits

Visit	Description	≈ Duration
1	Informed consent, eligibility criteria, baseline data, trial fitting 1, dispense lenses. Study lenses to be worn 13-15 days to first follow-up visit.	2.0 hours
3	13-15 day follow-up for the study lens, subjective responses, preference to habitual lenses, VA, fitting characteristics, surface characteristics, physiology, Final Evaluation.	1.0 hours

## **5. TEST ARTICLE ALLOCATION AND MASKING**

### **5.1. Test Article Allocation**

Use of the test articles will be randomized using a lens fitting schedule supplied by the study biostatistician. The clinical site will follow the lens fitting schedule provided and will complete enrollment according to the randomization list and will not pre-select or pre-assign subjects.

Randomly-permuted block randomization will be used to avoid bias in the assignment of subjects to treatment and to enhance the validity of statistical comparisons across treatment groups. A computer-generated randomization scheme will be used to randomly assign subjects, in blocks of 2, to one of the two lens groups (Test or Control). The randomization will be

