# **Clinical Study Protocol**

## **Johnson & Johnson Vision Care, Inc.**

stratified by site and type of habitual lens wear (daily disposable and daily wear reusable). The ratio of habitual wearers of daily disposable lenses to habitual wearers of daily wear reusable lenses is 7:3 within each study site (7 habitual wearers of daily disposable lenses versus 3 habitual wearers of daily wear reusable lenses). See Table 1. The random scheme will be generated using the PROC PLAN procedure from Statistical Analysis System (SAS) Software Version 9.4 or higher (SAS Institute, Cary, NC).

Randomization will be performed at visit 1. The following must have occurred prior to randomization:

- Informed consent must have been obtained.
- The subject must have met all eligibility criteria.
- The subject's screening and baseline information must have been collected.

When dispensing test articles, the following steps should be followed to maintain randomization codes:

1. Investigator or designee (documented on the Delegation Log) will consult the lens fitting schedule to obtain the test article assignment for that subject prior to dispensing.
2. Investigator or designee will record the subject's number on the appropriate line of the lens fitting schedule.
3. Investigator or designee will pull the appropriate test articles from the study supply. All test articles that are opened, whether dispensed (placed/fit on eye or dispensed outside the clinical site) or not, must be recorded on the Test Article Accountability Log in the "Dispensed" section.

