### **5.2. Masking**

This is a single-masked trial. The investigators may be aware of the study lenses based on a slight difference in lens color (the Test lenses will be slightly more turquoise in color than the Control lens).

Masking will be used to reduce potential bias. Subjects will be unaware of the identity of the investigational product. Investigators and clinical site personnel involved in the data collection will not be masked as to the identity of the investigational product.

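### Fixed blocks of 2 within site-by-habitual-lens strata let unmasked staff who track assignments know about 45–50% of them in advance, and no concealment of the schedule is described

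*Combined protocol and SAP*

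**What the plan says.** Section 5.1 gives the purpose of the method: "Randomly-permuted block randomization will be used to avoid bias in the assignment of subjects to treatment". It then names one block size: "A computer-generated randomization scheme will be used to randomly assign subjects, in blocks of 2, to one of the two lens groups". The scheme is "stratified by site and type of habitual lens wear", with a 7:3 ratio of daily disposable to reusable wearers within each site. Section 3.4 expects about 16 sites of about 20 subjects, about 10 on each lens.

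At the site, the investigator or a designee "will consult the lens fitting schedule to obtain the test article assignment for that subject prior to dispensing" and enters the subject number on the matching line. Consent, eligibility and baseline data must be complete before randomization, and sites are told not to pick or assign subjects beforehand.

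On masking, Section 5.2 says: "Investigators and clinical site personnel involved in the data collection will not be masked as to the identity of the investigational product". Section 5.3 covers masking of subjects by over-labelling and the breaking of the mask. No section describes sealed lines, central assignment or line-by-line release. Section 4.2 nevertheless claims: "Randomization eliminates the selection bias and balances both the known and unknown confounding factors that may affect the study outcomes".

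**The concern.** Random allocation protects against selection bias only if the people who recruit cannot foresee the next assignment. Here the block size is printed in the protocol that sites hold, staff are not masked, and the site keeps the running record. That is enough to deduce the second assignment of every pair.

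The existing rules do not prevent this. The ban on pre-selection governs conduct. The eligibility-first rule orders the steps. Neither hides an assignment that can already be worked out before the second subject is called.

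The opening is limited but real. Most entry criteria are factual or measured. Judgement remains in whom to call from the site's own database and when, and in two criteria: "Appear able and willing to adhere to the instructions set forth in this clinical protocol" and "or any other ocular abnormality that may contraindicate contact lens wear". Habitual lens type is known before the visit, so a candidate can be placed in a stratum in advance.

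At stake is the comparability of the arms on the four primary hypotheses, all of which must be met (Section 2.3). Under Section 14.5 the CLUE vision model adjusts for the baseline score. The logMAR model names no baseline acuity, and the fit and slit lamp models contain lens only. Covariate adjustment therefore gives limited cover on three of the four. Unmasked grading after assignment is a separate matter and is not addressed here.

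**Working it through.** **Inputs.** Block size 2, 1:1, strata site × habitual lens type (Section 5.1); 7:3 ratio (Sections 3.4 and 5.1); up to 16 sites of about 20 (Sections 3.4 and 4.3); CLUE vision difference +2, SD 21, margin −5, two-sided 0.05 (Section 14.2).

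**The plan's own figures.** 16 × 20 = 320. At 7:3 a site has 14 + 6; over 16 sites this is 224 + 96, or 112 + 48 per arm, as in Table 1. CLUE vision power by the noncentral t, with distance from the margin 2 + 5 = 7, is 80.2% at 143 per arm. This agrees with the 80% at 286 in Table 11. The protocol gives no figure for predictability.

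**Predictability with blocks of 2.** In a stratum of n, the assignments known in advance number floor(n/2). The share guessed correctly is known + ½ × (1 − known), because the first of each pair is a coin flip.

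| Site split | Known per site | Share known | Of 320 | Share guessable |
|---|---|---|---|---|
| 14 + 6 | 7 + 3 = 10 | 50% | 160 | 75% |
| 13 + 7 | 6 + 3 = 9 | 45% | 144 | 72.5% |
| 15 + 5 | 7 + 2 = 9 | 45% | 144 | 72.5% |

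**Predictability with blocks drawn independently from 4 and 6, equally likely.** The assumed observer knows those two sizes and every past assignment in the stratum. An assignment is certain if its probability is 0 or 1.

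For the first six subjects this can be done by hand. In a block of 6, three identical lenses at the start have probability 2/20, so ½ × 2/20 = 0.05 overall; positions 4, 5 and 6 are then certain. A third identical lens that first appears at position 4 has probability ½ × 6/20 = 0.15; positions 5 and 6 are then certain. For n = 6 the certain share is (0.05 + 0.20 + 0.20)/6 = 0.075. For n = 5 it is (0.05 + 0.20)/5 = 0.050.

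Exact enumeration extends this to longer strata:

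| n | Certain | Guessable |
|---|---|---|
| 14 | 0.0591 | 0.681 |
| 6 | 0.0750 | 0.672 |
| 13 | 0.0598 | 0.673 |
| 7 | 0.0643 | 0.657 |
| 15 | 0.0588 | 0.676 |
| 5 | 0.0500 | 0.643 |

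Per site of 20, and over 320:

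- 14 + 6: 1.2775 certain, 6.4%, 20.4 of 320; 67.8% guessable.
- 13 + 7: 1.2275 certain, 6.1%, 19.6 of 320; 66.7% guessable.
- 15 + 5: 1.1325 certain, 5.7%, 18.1 of 320; 66.75% guessable.

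**Price in balance.** Trials of 32 strata were simulated. At 14 + 6 per site the 95th percentile of the trial-wide Test–Control difference is 10 subjects, against 0 with blocks of 2. At 13 + 7 or 15 + 5 it is 12, against 10–12. A stratum that stops mid-block can differ by up to 3, against 1 now. At 14 + 6, about 36% of sites would not be exactly 10/10, though only about 2% would differ by more than 2.

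**Price in power.** CLUE vision power is 80.2% at 143/143, 80.2% at 138/148 and 80.1% at 135/151.

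**The case against.** **The counts are conditional.** Table 1 allows 286–320 randomized, and Section 4.3 counts a subject as enrolled at consent. A site of 18 split 13 + 5 gives (6 + 2)/18 = 44.4%, just under the quoted range. This stands: read the range as about 45–50% and the counts as those at 20 per site. The mechanism is unchanged.

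**Concealment may be described elsewhere.** The lens fitting schedule comes from the biostatistician and is not among the documents, so release instructions could accompany it. This stands too, and the gap is therefore one of description. It would not cure blocks of 2: with concealed lines, the second of each pair can still be deduced.

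**Sites may work from codes.** Section 5.2 says first that investigators may recognise the lens by color and then that they are not masked. Section 5.3 mentions randomization codes on labels, and Section 13.4.1 lets the investigator break the code. The wording should be reconciled, but with two lenses of visibly different tint a code gives little protection.

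**The opportunity is narrow and blocks of 2 have a purpose.** Enrollment lasts four weeks per site, most criteria are measured, and CLUE vision adjusts for baseline. Blocks of 2 also serve the aim of 10/10 per site. All of this is fair and limits the severity. It is also true that correct guessing falls only from 75% to 67.8% with 4/6 blocks, so the block change is not sufficient alone, and 4 and 6 are one reasonable choice rather than the only one.

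**Conclusion.** The concern holds. Under Section 5.1 as written, staff who know the block size and track assignments by stratum know 50% of assignments in advance at 14 + 6 per site, and 45% if both strata end on odd counts. They would guess 72.5–75% correctly. If the schedule is an open list, the share visible could be higher; the documents neither say so nor exclude it.

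The claims in Sections 4.2 and 5.1 about avoiding selection bias are therefore not secured for the second subject of each pair. The finding concerns exposure to bias. It does not show that steering would occur, and no shift in CLUE points or any other endpoint is claimed. The change should be made because the weakness comes from the stated block size itself and is cheap to correct.

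**What to change.** Revise Section 5.1 in three ways.

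1. State that each assignment is released singly, after consent, eligibility and baseline are recorded. Use the EDC if it can do this, otherwise sequentially sealed lines. The order of steps is already in the plan; the one-at-a-time release is new.
2. Keep the stratification, but replace fixed blocks of 2 with sizes drawn independently at random, for example from 4 and 6. Make each stratum's list long enough for over-enrollment and for the replacements foreseen in Sections 4.3, 5.3 and 8.2.
3. Remove the block sizes from the protocol and hold them in a document that sites do not have.

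Release and block size are both needed. Release alone leaves the second of each pair known, and larger blocks alone do not conceal an open list.

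The cost is a new PROC PLAN list, a separate randomization document and a release step; whether the EDC supports release is not stated. Site balance becomes approximate rather than near exact. Sample size and analysis models stay as they are.
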